10.5.1 Efficacy Analyses

The primary and key secondary efficacy analyses that compare ZX008 to placebo will be performed using subjects from Cohort 2 only. Efficacy endpoints, such as convulsive seizure frequency, assessed in Cohort 1 during the Transition Period will be summarized with descriptive statistics only.

10.5.1.1 Primary Efficacy Analysis – Cohort 2

The primary efficacy endpoint is the change in the mean convulsive seizure frequency (MCSF) per 28 days between the Baseline and T + M periods. The MCSF will be calculated from all available data collected during the Baseline or T + M Periods.

The primary endpoint will be analyzed using an analysis of covariance (ANCOVA) model with treatment group (ZX008 or placebo) and age group (< 6 years, \geq 6 years) as factors, and with baseline frequency as a covariate. The primary analysis will compare the ZX008 group to the placebo group using a two-sided test at the $\alpha=0.05$ level of significance.

Since the ANCOVA used in the primary analysis relies on assumptions of normality, the primary endpoint will also be analyzed using a nonparametric method that does not require as stringent assumptions. A nonparametric test will be used to compare the ZX008 group to the placebo group while stratifying for age group. If normality assumptions are not met, the results of the nonparametric test will be used to assess the primary objective.

Additional analyses will compare the percentage changes between the baseline MCSF and the MCSF measured independently during the Titration Period alone and the Maintenance Period alone.

10.5.1.2 Key Secondary Analyses – Cohort 2

The first key secondary endpoint – the proportion of subjects who achieve a $\geq 50\%$ reduction from baseline in convulsive seizure frequency – is derived directly from the primary endpoint. That is, the proportion of subjects in the ZX008 group who have a change in convulsive

frequency of at least 50 percentage points will be compared to the analogous proportion in the placebo group. The comparison will be made using a logistic regression model that incorporates the same factors and covariates as the ANCOVA used in the primary analysis. The analyses will be performed using data collected over the T + M period.

The longest interval between convulsive seizures will be calculated for each subject over the entire T + M period. The ZX008 and placebo groups will be compared using a Wilcoxon test.

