6. STATISTICAL METHODOLOGY

6.1 STATISTICAL AND ANALYTICAL ISSUES

6.1.1 Statistical Methods

Tabulations will be produced for demographics, baseline, efficacy, and safety parameter. Continuous data will be summarized using descriptive statistics including the number of observations, means, standard deviations, medians, lower and upper quartiles, and ranges. Categorical variables will be summarized showing number of observations, frequencies, and percentages.

This SAP provides summary of statistical methods for comparing the regimens in the double-blind study (cohort 2).

Confidence intervals will be calculated at the 95% confidence level for key parameters or estimates as described in the sections below. Two-sided statistical significance testing (alpha level = 0.05) comparing treatment to placebo will be performed for the primary and secondary endpoints as described in the respective sections below.

All statistical analyses and summaries will be performed using SAS statistical software (Version 9.3 or later version that will be in use at the time of analysis, unless otherwise noted). Adverse events will be coded using the most recent MedDRA version available at the time of analysis and the actual version used will be footnoted in the respective adverse events summary tables. Concomitant medications will be coded using the available recent version of World Health Organization (WHO) Drug dictionary and the version used will be footnoted in the respective medications summary tables.

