6.1.2 Multiplicity Strategy and Testing Hierarchy

The multiplicity issues in the statistical inference in this study arise from multiple endpoints.

The efficacy analyses will employ a serial gatekeeper strategy to maintain the Type 1 error rate at $\alpha = 0.05$ across the family of analyses that support the primary and key secondary objectives.

All statistical analyses will be performed and results tabulated with test statistics, p-values, and/or 95% confidence intervals.

Formal statistical testing will be performed for one primary endpoint and two key secondary endpoints for the comparison of ZX008 0.5 mg/kg with Placebo. In order to preserve the overall Type 1 error rate at $\alpha = 0.05$, these tests will proceed as follows:

Step 1: The primary efficacy endpoint (mean convulsive seizure frequency per 28 days) will be formally tested first between the ZX008 0.5 mg/kg and Placebo group. If the comparison is statistically significant at $\alpha = 0.05$ (2-sided) level, the hypothesis testing will proceed to Step 2. Otherwise formal testing of the other hypotheses stops.

Step 2: The secondary efficacy endpoint (proportion of subjects who achieve a $\geq 50\%$ reduction from baseline in convulsive seizure frequency) will be compared between the ZX008 and Placebo

group. If the comparison is statistically significant at $\alpha = 0.05$ (2-sided) level, hypothesis testing will proceed to Step 3. Otherwise formal testing of the other hypotheses stops.

Step 3: The endpoint longest convulsive seizure-free interval endpoint will be compared between ZX008 and Placebo using a significance level of $\alpha = 0.05$ (2-sided).

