6.3.1.1 Primary Analysis Tests

T + M Period:

The primary analysis will compare the ZX008 0.5 mg/kg/day group to the placebo group using a two-sided test at $\alpha = 0.05$ level of significance.

The primary endpoint (CSF_{T+M}) will be analyzed using an analysis of covariance (ANCOVA) model with treatment group (ZX008 or Placebo) and age group (< 6 years, ≥ 6 years) as

classification factors, log baseline frequency (CSF_B) as a covariate in the model, and log CSF_{T+M} as response. Treatment group means and the difference from placebo will be estimated with least squares means from the analysis model along with 95% confidence intervals and associated 2-sided p-values. Estimated treatment group means and CI endpoints will be exponentiated for presentation.

The null hypothesis

$$H_0: \mu_{Z008} - \mu_P = 0,$$

will be tested against the alternative

$$H_A: \mu_{Z008} - \mu_P \neq 0,$$

where μ_{Z008} and μ_P represent the ZX008 0.5 mg/kg and Placebo group means (on the log scale), respectively.

Rejection of the null hypothesis in favor of the alternative, in the presence of a statistically significantly bigger reduction in mean convulsive seizure frequency from baseline for the treatment group compared to the placebo group, (two-sided p-value < 0.05) will be regarded as evidence of a treatment benefit in favor of ZX008 0.5 mg/kg group.

Sample SAS code for the ANCOVA described above is as follows:

```
proc glm data=temp;
  class agegrp trtp;
  model csftm = bcsf agegrp trtp / SS3;
  lsmeans trtp / pdiff stderr;
```

where trtp = randomized treatment group (with codes 1, 2 indicating placebo, and 0.5 mg groups).

bcsf = log(CSF_B),
csftm = log(CSF_{T+M})
agegrp = age group.

Additional statements may be used to obtain estimates and 95% confidence interval. Endpoints of the CIs may be exponentiated to obtain CI on the original scale. Fitted values and residuals may be plotted to check model assumptions.

Since the ANCOVA used in the primary analysis relies on assumptions of normality, the primary endpoint will also be analyzed using a nonparametric method that does not require as stringent assumptions. A nonparametric ANCOVA will be used to analyze the data, with ranks of the baseline CSF_B as a covariate and ranks of CSF_{T+M} as response. If normality assumptions are not met, the results of the nonparametric test will be used to assess the primary objective.

Treatment by Baseline Seizure Category:

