8. APPENDICES

 APPENDIX 1: List of Tables, Figures, and Listings

Table/ Figure/ Listing	Number	Table Header
	14.1	Demographic data and other baseline characteristics
	14.1.1	Subject disposition
Table	14.1.1.1b	Overall Subject Disposition – All Enrolled Subjects
Table	14.1.1.2b	Major Protocol Deviations – Safety Population
Table	14.1.1.3b	Study Populations
	14.1.2	Demographic and other baseline characteristics
Table	14.1.2.1b	Demographic and Baseline Characteristics – Safety Population
Table	14.1.2.2b	Demographic and Baseline Characteristics – mITT Population
	14.1.3	Medical history
Table	14.1.3.1b	Medical History– Safety Population
	14.1.4	Prior and concomitant medication/treatment
Table	14.1.4.1b	Prior Medications and Therapies/Treatments – Safety Population
Table	14.1.4.2b	Concomitant Medications and Therapies/Treatments – Safety Population
Table	14.1.4.3b	Prior Antiepileptic Treatment – Safety Population
Table	14.1.4.4.1b	Concomitant Antiepileptic Treatment – Safety Population
Table	14.1.4.4.2b	Number of Subjects by Number of Concomitant Antiepileptic Treatments – Safety Population
	14.1.5	Treatment Exposure and compliance
Table	14.1.5.1b	Duration of Treatment Exposure – Safety Population
Table	14.1.5.2b	Compliance to IMP Intake – Safety Population
	14.2	Efficacy, pharmacokinetics, and pharmacodynamics
	14.2.1	Efficacy – ZX008 vs Placebo
Table	14.2.1.1.1b	Convulsive Seizure Frequency per 28 Days: Summary Statistics – mITT Population
Table	14.2.1.1.2b	Convulsive Seizure Frequency per 28 Days: Summary Statistics by Age Group – mITT Population
Table	14.2.1.2b	Convulsive Seizure Frequency per 28 Days : Parametric Analysis – mITT Population
Table	14.2.1.3b	Convulsive Seizure Frequency per 28 Days : Nonparametric Analysis – mITT Population
Table	14.2.1.4b	Percentage Change in Convulsive Seizure Frequency per 28 Days: Parametric Analysis – mITT Population

Table	14.2.1.5b	Percentage Change in Convulsive Seizure Frequency per 28 Days: Nonparametric Analysis – mITT Population
Table	14.2.1.6b	Mean Convulsive Seizure Frequency – Exploratory Efficacy Analysis of Subjects who are SCN1A Mutation Positive – mITT Population
Table	14.2.1.7b	Convulsive Seizure Frequency per 28 Days: Parametric Analysis – PP Population
Table	14.2.1.8b	Convulsive Seizure Frequency per 28 Days: Nonparametric Analysis – PP Population
Table	14.2.1.9b	Percentage Change in Convulsive Seizure Frequency per 28 Days: Parametric Analysis - PP Population

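### The rule for switching the primary test from log ANCOVA to a nonparametric test has no criterion and need not be applied before unblinding

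*SAP*

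**What the plan says.** SAP 6.3.1.1 defines the primary model as an ANCOVA with treatment and age group as factors, "log baseline frequency (CSF_B) as a covariate in the model, and log CSF_{T+M} as response". It then says that the endpoint will also be analysed by a nonparametric ANCOVA, "with ranks of the baseline CSF_B as a covariate and ranks of CSF_{T+M} as response", and gives the switch: "If normality assumptions are not met, the results of the nonparametric test will be used to assess the primary objective". The only model check described is optional: "Fitted values and residuals may be plotted to check model assumptions".

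Protocol 10.5.1.1 and the protocol synopsis contain the same switch. The protocol describes the fallback differently: "A nonparametric test will be used to compare the ZX008 group to the placebo group while stratifying for age group".

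SAP Appendix 1 plans a parametric table (14.2.1.2b) and a separate table (14.2.1.3b) titled "Nonparametric Analysis – mITT Population", so both results will exist whatever the residuals look like.

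SAP 6.1.1 sets the level: "Two-sided statistical significance testing (alpha level = 0.05) comparing treatment to placebo will be performed for the primary and secondary endpoints". SAP 6.1.2 makes the primary test the gate to the two key secondary tests: "The efficacy analyses will employ a serial gatekeeper strategy to maintain the Type 1 error rate at" 0.05.

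**The concern.** A switch between two valid tests keeps its level when the trigger is fixed and does not depend on the results. Here the trigger is a phrase. No test, statistic, cut-off, decision-maker or time point is given. The sample SAS code fits treatment, so residuals from that model need the treatment codes unless a blinded version is specified.

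Elsewhere the SAP does tie a choice to the blind: section 5.1.4 finalises the per-protocol exclusions before unblinding. It does not do so for this choice, which matters more.

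At stake is the error rate claimed for the whole hierarchy, since this test opens it. There is also a practical cost. If the two tests fall on opposite sides of 0.05, the sponsor cannot show from the plan which one was meant to decide.

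**Working it through.** **1. The plan's own figure.** Protocol 10.1 assumes a difference of 40 percentage points, SD 58, two-sided alpha 0.05 and 90% power.

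n per arm = 2(1.960 + 1.282)² × SD²/difference² = 21.01 × 58²/40² = 44.2, rounded up to 45, as stated.

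SAP 6.1.10 uses SD 55: 21.01 × 55²/40² = 39.7, rounded up to 40, as stated.

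Both sizes are used below. The difference between them is a separate matter.

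**2. Type I error by simulation under no effect.** There were 20,000 trials per row (Monte Carlo standard error √(0.05 × 0.95/20,000) = 0.15 points), with 1:1 allocation within age group.

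- From the documents: the arm sizes, 40% of subjects in the younger stratum, and a baseline of at least 4 per 28 days (6 seizures in 42 days: 6 × 28/42 = 4).
- Assumed, because the documents give no distribution: log baseline = log 4 + Gamma(1.5, 0.8); slope 0.9 on log baseline; errors normal (SD 0.7), 0.5 × t(3), or 0.7 minus an exponential of mean 0.7; alternatively over-dispersed counts analysed as log(y+1). No age effect.

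The fixed rule in the table is: if Shapiro-Wilk on the model residuals gives p < 0.05, use the rank test. All entries are percentages.

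| Errors, n per arm | Log ANCOVA | Rank ANCOVA, no age term | Fixed rule | Tests disagree | Smaller p always used |
|---|---|---|---|---|---|
| Normal, 45 | 4.74 | 4.73 | 4.76 | 3.69 | 6.58 |
| t(3), 45 | 4.86 | 4.88 | 5.08 | 3.91 | 6.83 |
| Left-skewed, 45 | 4.81 | 4.83 | 4.83 | 3.99 | 6.82 |
| Counts, 45 | 4.93 | 4.86 | 4.86 | 3.62 | 6.71 |
| Normal, 40 | 4.99 | 5.03 | 5.00 | 3.50 | 6.76 |
| Left-skewed, 40 | 4.89 | 5.01 | 5.01 | 4.16 | 7.03 |

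The last column can be checked by an identity: P(either rejects) = [P(log) + P(rank) + P(disagree)]/2. For the first row, (4.74 + 4.73 + 3.69)/2 = 6.58.

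Two independent 5% tests would give 1 − 0.95² = 9.75%. That bound does not apply, because the two tests are strongly correlated.

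**3. Other assumed settings.** Further simulations with different baseline and error assumptions gave 5.8-6.8%, 6.4-6.7% and 6.6-7.8% when the smaller p is always used. A Shapiro-Wilk rule on the residuals gave 4.4-5.2% in one setting and 5.1-5.7% in another. The same rule on residuals from a model without treatment gave 4.9-5.1%. Over all settings, then, a fixed rule gives 4.4-5.7%, and always taking the smaller p gives 5.8-7.8%.

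**4. The fallback.** The protocol stratifies by age group. The SAP sentence names only baseline and response ranks. Where the SAP spells out the analogous rank ANCOVA for other endpoints (6.3.3.3 and 6.3.3.6), it lists treatment and baseline ranks and again no age. SAP 6.9 does not list this as a change from the protocol. Leaving age open as a further choice raises the worst case only slightly: from 6.6-7.0% to 6.6-7.1% in the runs tabulated, and from 6.4-6.7% to 6.8-7.0% in another setting.

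**5. Whether a switch is likely.** SAP 6.3.2.2 plans for subjects with no convulsive seizures. For them the log response is undefined, and 6.3.1.1 gives no offset. Ranks have no such problem, so the fallback could come into play and the two tests could include different subjects.

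**The case against.** The strongest reply is that the plan makes the switch depend on normality, not on p-values. Followed honestly, it holds about 5%. The inflation appears only if someone takes the smaller p whatever the residuals show, which would depart from the rule as written. This stands, and it limits the point to an undefined criterion and timing. A nonparametric fallback is not itself a fault.

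A reader might infer that the choice will be made after unblinding. The documents do not say so. They give no time for the check, and the sentence on residual plots is not expressly linked to the switch. Only the weaker statement holds: nothing prevents it.

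The SAP does give a default. It calls the log ANCOVA the one used in the primary analysis, and 6.3.1.2 makes the mITT primary analysis the efficacy criterion. But 6.3.1.2 does not say which test that is once the switch applies, so the default does not close the gap.

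A reader might also infer that a rank-based decision would leave the primary objective without an effect estimate. That is not supported. SAP 6.3.1.1 plans exponentiated least-squares means and 95% confidence intervals without making them conditional on normality, and both tables are planned. At most, no estimate is explicitly paired with the rank test.

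Finally, a reader might expect the two tests to disagree often when the drug works. At about the planned effect (40/58 = 0.69 SD), simulated disagreement on significance was about 4-7%. That is enough to matter in a given trial, but it would not be common.

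**Conclusion.** The concern holds as a gap in pre-specification. The test that gates the 0.05 hierarchy can change on a criterion that is not stated, at a time that is not fixed, with both results available. The fallback is also described differently in the two documents.

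The size is bounded. Type I error is about 5% under any fixed rule. It is about 6-8% in the worst case, where the more favourable result is always used, an excess of roughly 1 to 3 points. These figures rest on assumed error shapes and baseline distributions, since the documents give none. They describe what the text leaves open, not what the sponsor intends or did. The gap should be closed before unblinding; it does not make either test invalid.

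**What to change.** Preferred: name one test as primary without condition in SAP 6.3.1.1 and make the other a sensitivity analysis.

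Otherwise keep the switch but fix it. State the normality test and cut-off, apply it to pooled blinded residuals from the model without the treatment term, and record the resulting choice in a signed note before unblinding.

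In either case:

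- include age group in the rank ANCOVA, so that protocol and SAP agree;
- state that the already planned back-transformed log-ANCOVA estimate and 95% confidence interval will be reported beside the deciding test;
- state how a zero seizure frequency enters the log model, since without this neither the residual check nor the estimate can include such subjects.

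The cost is a few SAP sentences and, for the second option, one blinded check. The sponsor loses discretion. The blinded check also detects non-normality somewhat less well when the drug works: with t(3) errors, simulated Shapiro-Wilk detection fell from 82% to 71% at an effect of 0.7 SD and to 52% at 1.2 SD. Naming one test outright avoids that cost.

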Subjects who complete all of the Maintenance Period and will not be continuing into the open-label extension study, and subjects who discontinue from the study early, will be tapered off of study medication. Study medication will continue to be administered as equal doses BID in the morning and in the evening approximately 12 hours apart, with food. Each dose should be separated by a minimum of 8 hours and a maximum of 12 hours. A missed dose of study medication may be taken later up to 8 hours before the next scheduled dose; otherwise, the missed dose should not be given. IMP will be administered using the oral dosing syringe provided.

The taper algorithm is indicated below.

Table 3. Taper Algorithm

Randomized Dose	Taper Step 1 Day 1-4 after study completion or early termination	Taper Step 2 Days 5-8 after study completion or early termination	Taper Step 3 Days 9-14 after study completion or early termination
ZX008 0.5 mg/kg/day	ZX008 0.4 mg/kg/day	ZX008 0.2 mg/kg/day	No study drug administration
Placebo	Placebo	Placebo	No study drug administration

Note: maximum daily dose of ZX008 is 20 mg.

Transition Period:

Subjects who complete the Maintenance Period and will be continuing into the open-label extension study will be transitioned from double-blind study medication to open-label ZX008 (hypothetical transition is depicted in [Table 4](#)). Study medication will be administered as equal doses BID in the morning and in the evening approximately 12 hours apart, with food. Each dose should be separated by a minimum of 8 hours and a maximum of 12 hours. A missed dose of study medication may be taken later up to 8 hours before the next scheduled dose; otherwise, the missed dose should not be given. Study medication will be administered using the oral dosing syringe provided.

All subjects entering the open-label extension study will be transitioned from their blinded daily dose (placebo, or assigned dose of ZX008) to the 0.2 mg/kg dose during the interval between Visits 12 and 13, without breaking the blind. The IVR/IWR system will assign two bottles of IMP to the subject, one for each step in the transition. A new bottle of IMP will be started by the subject at each level of the transition step.

Table 4. Transition Algorithm

Randomized Dose Selected for Cohort 2	Step 1 Days 1-7 after study completion	Step 2 Days 8-14 after study completion
--	---	--

ZX008 0.5 mg/kg/day	ZX008 0.4 mg/kg/day	ZX008 0.2 mg/kg/day

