- d: The Visit 8 ECHO must be performed any time between Study Day 40 and Study Day 54. The Visit 12 ECHO must be performed any time between Study Day 90 and Study Day 113; if a subject discontinues early from the study, the ECHO should be scheduled as soon as practical. If the Study Day 43 ECHO was completed ≤ 30 days prior to early termination, the Visit 12 ECHO will not be performed provided the parent/guardian agrees to bring the subject to the clinic for the cardiac follow-up visit.
- e: Females of child-bearing potential
- f: Plasma sample for PK assessment will be conducted prior to the dose at the Follow-up visit and 1, 2, and 4-6 hours after dose administration for Subjects continuing into the open-label extension trial.
- g: Plasma sample for assessment of background AED(s) will be conducted prior to the dose of AED(s) at Visits 3, 6, 8 and 12.
- h: Study drug/diary dispensed for the transition for subjects entering the open-label extension trial and for tapering for subjects exiting the study.
- i: Site personnel will review study medication dosing procedure (titration) with parent/caregiver.
- j: Study drug administration begins in the morning of Study Day 1.
- k: Only adverse events related to cardiac safety will be collected at this visit.
- l: Mandatory one time collection any time during or after screening and before Visit 10.

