6.1.6 Visit Windows

The following rules will be used to window data into treatment periods tabulations. For all by-visit tabulations, the nominal visit as recorded on the CRF will be used.

Double Blind Treatment Period	The Double-Blind Treatment Period start date is the date of first dose. The Double-Blind Treatment Period end date is the last date the patient was on study treatment. The Double-Blind Treatment Period includes time from first
-------------------------------	---

	treatment start date, which includes 21 days of Titration period, 12 weeks of Maintenance period and Taper/Transition period (14 days) - For subjects who discontinue early from the study, the double-blind treatment period end date will be the date at the early termination visit (Visit 12).
Titration Period	The Titration Period covers up to the first 21 days of treatment while subjects are titrated to their randomized dose. It begins on the first day of treatment (Study Day 1) and extends through Visit 6 (when the patient has reached their randomization dose). The Titration Period applies to all subjects including placebo recipients. If a subject withdraws from the study prior to treatment in the maintenance period, all safety assessments and events up to and including the date of study withdrawal will be tabulated in the titration period.
Maintenance Period	The Maintenance Period covers the 12 weeks following the end of the titration period. It begins on the date of Visit 6 + 1 day and extends through the end of study/early termination visit (Visit 12).
Titration +Maintenance Period (T+M)	The T+M period combines the Titration and Maintenance periods, beginning on the date of first treatment (Study Day 1) and extending to the end of the 12 week Maintenance Period. The primary efficacy endpoint is calculated based on data from the T+M period.
Taper/Transition Period	The Taper/Transition period consists of approximate 14- days starting from end of study/early termination visit (Visit 12) + 1 day. For patients who are not entering into the open-label extension study, patients will gradually be tapered off of study medication. Patients entering the open-label extension study will first enter the transition phase where all patients will be on a dose of 0.2mg/kg/day at the end of this phase. The end date of this period is considered to be the date recorded at Visit 13.

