6.1.7 Handling of Dropouts and Missing Data

There will be no imputation of missing data for efficacy endpoints.

Seizure Diaries:

Seizures are recorded in the Daily Seizure Diary (DSD), while the End of Day Diary (EDD) provides Yes/No confirmation that that seizures were experienced for a specific date, or that the date was seizure free.

- If no seizures are entered in the DSD and the EDD confirms seizure freedom, the number of seizures for that date is zero.
- If seizures are entered in the DSD and the EDD states seizure freedom, the seizures recorded for that date supersede the EDD stating seizure freedom.
- If no seizures are entered in the DSD and there is no response in the EDD, that day will be considered to have missing diary data.

- If no seizures are entered in the DSD and there is a Yes response in the EDD, that day will be considered to have missing diary data.

Unless specified otherwise in the relevant sections describing analyses for individual parameters, missing diary data will not be imputed for efficacy variables. Hence for subjects missing some of the daily measurements, the available data will be used. No explicit imputation will be performed for subjects who drop out prior to end of study (Visit 12).

Handling of missing date information for AEs:

- The term *missing date* refers to a completely missing date or to an incomplete date/partial date where parts are not available, e.g. missing month/day/year.
- Missing start and end dates will be imputed conservatively, i.e. missing values will be imputed in such a way that the duration of the AE is considered with the longest possible duration and such that, whenever the AE may potentially start after first IMP, the AE will be handled as a TEAE.
- The missing start date and End date of AE will be imputed for the purpose of calculating treatment emergent status and assigning events to treatment periods using definitions given in the following table.

Handling of missing date information for AEs:

- The term *missing date* refers to a completely missing date or to an incomplete date/partial date where parts are not available, e.g., missing month/day/year.
- Missing start and end dates will be imputed conservatively, i.e., missing values will be imputed in such a way that the duration of the AE is considered with the longest possible duration and such that, whenever the AE may potentially start after the first dose of IMP, the AE will be handled as a TEAE.

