The primary analysis described above will be repeated with baseline seizure frequency as a categorical variable, rather than a covariate.

Baseline seizure frequency per 28 days will be categorized as either < 10; 10-50; or >50

M Period only:

The primary analysis described above will be repeated using data from the Maintenance period only as response. For subjects who did not reach the Maintenance period, their Transition period data will be used to represent their M period data.

A similar ANCOVA model will be used, and if distributional assumptions are not met, a nonparametric analysis will be performed.

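### The Maintenance-only repeat of the primary analysis fills gaps with Transition data, which subjects who never reached Maintenance either do not have or have only off their randomized regimen

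*SAP*

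**What the plan says.** SAP 6.3.1.1 repeats the primary ANCOVA with Maintenance data as the response and adds: "For subjects who did not reach the Maintenance period, their Transition period data will be used to represent their M period data".

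The periods are defined elsewhere:

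- **Transition** (SAP 3.2.2; Protocol 5.5.7 agrees): "Subjects who complete the Maintenance Period and will be continuing into the open-label extension study will be transitioned".
- **Taper** (SAP 3.2.2; Protocol 5.5.5 agrees): "subjects who discontinue from the study early, will be tapered off of study medication". Protocol Table 6 gives two four-day steps and then six days without drug.
- **Timing** (SAP 6.1.6): one joint Taper/Transition window of about 14 days, "starting from end of study/early termination visit (Visit 12) + 1 day", ending at Visit 13.
- **Diaries** (SAP 4, note h): "Study drug/diary dispensed for the transition for subjects entering the open-label extension trial and for tapering for subjects exiting the study".
- **Exception** (Protocol 4.8): a non-completer may be let into the extension case by case.

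On missing data, SAP 6.1.7 says: "Unless specified otherwise in the relevant sections describing analyses for individual parameters, missing diary data will not be imputed for efficacy variables". It also rules out explicit imputation for dropouts. For safety data only, SAP 6.1.6 assigns assessments of subjects who withdraw before Maintenance to Titration: "up to and including the date of study withdrawal will be tabulated in the titration period".

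Protocol 10.5.1.1 plans a Maintenance-only comparison with no substitution, and SAP 6.9 does not list this one among its changes from the protocol.

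**The concern.** The rule is written for the subjects who, by the plan's own definitions, normally have no Transition period. An analyst must therefore either follow a rule that does not work or make an undocumented choice.

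The Maintenance-only repeat is meant to show the effect at the stable randomized dose, and SAP 6.3.1.2 expects the supportive analyses to point the same way as the primary one. Filling part of it with days when placebo subjects take ZX008, or when ZX008 subjects step down or take nothing, works against that purpose.

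SAP 6.3 also repeats the key secondary analyses for Maintenance only and does not say whether the same substitution applies. For the longest seizure-free interval, a substituted short window would cap the value.

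**Working it through.** **Window position.** T+M is 21 + 84 = 105 days. Visit 12 is Day 106 and Visit 13 is Day 120, so for a completer the window is Days 107 to 120, which is 14 days and matches SAP 6.1.6. For a dropout, Visit 12 is the early termination visit and the window follows that.

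**Literal readings of the rule.**

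1. Transition as defined, tapered subject: no such period, so no value.
2. Transition as defined, non-completer admitted to the extension: placebo subjects receive ZX008 on 14 of 14 days under SAP Table 4, or 7 of 14 under Protocol Table 7. The two tables contradict each other and must be reconciled.
3. Joint Taper/Transition window, tapered subject: diary data can exist, but 6 of 14 days (43%) are drug-free.

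**Scheduled dose in each candidate window.** Mean mg/kg/day, before the 20 mg cap, from the Titration, Taper and Transition tables. The last two list only the 0.5 mg/kg/day row for ZX008, so that row is used.

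| Window | ZX008 | Placebo | Separation | Share of 0.50 |
|---|---|---|---|---|
| Maintenance | 0.50 | 0 | 0.50 | 100% |
| Transition, SAP Table 4 | (7×0.4 + 7×0.2)/14 = 0.30 | 0.20 | 0.10 | 20% |
| Transition, Protocol Table 7 | 0.30 | (7×0 + 7×0.2)/14 = 0.10 | 0.20 | 40% |
| Taper | (4×0.4 + 4×0.2 + 6×0)/14 = 0.171 | 0 | 0.171 | 34% |
| Titration, stops after Day 7 | 0.20 | 0 | 0.20 | 40% |
| Titration, stops after Day 14 | (7×0.2 + 7×0.4)/14 = 0.30 | 0 | 0.30 | 60% |
| Titration, all 21 days | (7×0.2 + 7×0.4 + 7×0.5)/21 = 0.367 | 0 | 0.367 | 73% |

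These compare windows; they are not effect estimates.

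**Illustration of size.** The documents give no dropout rate. Assume that the effect is proportional to dose separation and take the SAP's design values (40 per arm, SD 55, difference 40), with power = Φ(δ/(σ√(2/n)) − 1.96).

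- Plan's own figure: 40/(55√(2/40)) = 3.25, power 90.2%, which reproduces the stated 90%.
- k subjects per arm substituted: δ becomes 40(1 − f + f·s), with f = k/40 and s the share in the table for the Transition and Taper windows (20% to 40%). For k = 1, power is 89.0% to 89.3%; for k = 6, it is 81.7% to 84.1%.
- The same subjects left out instead: 89.5% for k = 1 and 85.1% for k = 6.

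**Precision if no substitution is made.** The standard error rises by √(n/(n−k)) − 1. For k = 1, 2, 3 (assumed) this is 1.3%, 2.6%, 4.0% with 40 per arm (SAP 6.1.10), or 1.1%, 2.3%, 3.5% with 45 per arm (Protocol 10.1).

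**Longest seizure-free interval.** Maintenance can give up to 84 days. A 14-day window is 14/84 = 17% of that, and a 21-day window is 21/84 = 25%.

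**The case against.** The strongest reply is that this is a wording slip with little consequence. SAP 6.4.1 joins the words titration and transition when it names the period ending at Visit 13, and subjects who stop before Maintenance do have Titration data. The analysis is supportive, SAP 6.3.1.2 makes the mITT primary analysis the main criterion, and the table list in SAP Appendix 1 titles no Maintenance-only seizure-frequency table. All of that is fair and limits the weight. It does not remove the problem: the sentence names a different, separately defined period.

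Other points that stand in part:

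- The joint Taper/Transition window can be programmed. The objection to it is that the data are unsuitable.
- Tapered placebo subjects never receive ZX008; they have eight days of placebo and then nothing.
- At 50 kg or more (20/0.4), the 20 mg cap makes the 0.4 step equal to the full dose.
- SAP 3.2.2 introduces Table 4 as hypothetical, but the text after it states definitely that placebo subjects start ZX008 on Day 1.
- Protocol 4.5 lets the investigator stop drug at once instead of tapering, so 34% describes one schedule. Immediate stopping would make the window less suitable still.
- Titration stopped after Day 7 has the same 40% separation as Transition under Protocol Table 7. The case for Titration is that both arms are then on their randomized double-blind treatment, not that dilution is always slight.
- The rule sits under the primary analysis, so its extension to the key secondary endpoints is an open question and not something the SAP states.
- SAP 6.1.7 allows exceptions set out in individual sections, so there is no firm contradiction with its no-imputation statement.

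**Conclusion.** The concern holds. As written, the rule yields no value or a value that does not represent randomized treatment at the Maintenance dose, under every literal reading. That Titration was intended is a reasonable inference, but only the sponsor can confirm it.

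The weight is minor to moderate. Only the supportive mITT Maintenance-only repeat is affected. The primary T+M test and the testing hierarchy do not use the rule, and the PP population already requires at least four weeks of Maintenance. The bias is likely small, but its size and direction cannot be fixed: the number of early leavers is not given, and they may be atypical, since worsening seizures is a listed reason to discontinue (Protocol 4.5). The power figures rest on the assumed proportionality and the assumed counts.

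**What to change.** Before unblinding, delete the reference to Transition data in SAP 6.3.1.1 and choose one of these:

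1. **Name Titration.** Suggested text: 'For mITT subjects who did not reach the Maintenance period, the M-period CSF is calculated from their double-blind Titration diary data up to discontinuation; the number of such subjects is reported by arm.' This keeps every mITT subject who has Titration diary data and stays on randomized treatment. The cost is dilution: scheduled dose averages 73% of 0.5 mg/kg/day over a full Titration, and 40% if the subject stops after Day 7.
2. **Make no substitution**, and report the number excluded by arm. The result is then conditional on reaching Maintenance, with the small loss of precision shown above.

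Either way, state whether the rule applies to the Maintenance-only repeats of the key secondary endpoints, with a separate statement for the longest seizure-free interval. List any substitution that is kept in SAP 6.9. Reconcile SAP Table 4 with Protocol Table 7. Apart from that reconciliation, the cost is one or two SAP sentences and one derivation line.
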